## **6.1.2 Study Days**

### **Study Days (Days Relative to the First Dose of Study Drug)**

Study days are calculated for each time point relative to the first dose of study drug. Study days are negative values when the time point of interest is prior to the first study drug dose day. Study days are positive values when the time point of interest is after the first study drug dose day. There is no Study Day 0. Study Day 1 is the day of the first dose of study drug.

### **Study Drug End Days (Days Relative to the Last Dose of Study Drug)**

Study drug end days are calculated for each time point relative to the last dose of study drug. The last day of study drug dosing is defined as Study Drug End Day 0. Days before it have negative study drug end days and days after it have positive study drug end days.

### **Final Treatment Value**

The final treatment value is defined as the last non-missing measurement collected after Study Day 1 and on or before Study Drug End Day 2.

### **Final Post-Treatment Value**

The final PT value for each subject is the last non-missing measurement collected after Study Drug End Day 2 and on or before Study Drug End Day 999.

## **6.2 Definition of Analysis Windows**

For efficacy analyses of HCV RNA and resistance, the time windows specified in [Table 1](#) and [Table 2](#) describe how efficacy data are assigned to protocol-specified time points during the Treatment and PT Periods, respectively. All time points and corresponding time windows are defined based on the date/time of blood sample collection.

For safety laboratory data, vital signs, Child-Pugh score, and PRO instruments, the time windows specified in [Table 1](#) and [Table 3](#) describe how data are assigned to protocol-specified time points.

For samples of plasma HIV-1 RNA and flow cytometry (including but not limited to CD4+ T-cell and CD8+ T-cell counts [absolute and percent]), the time windows specified in [Table 4](#) and [Table 5](#) describe how data are assigned to protocol-specified time points.

If more than one assessment is included in a time window, the assessment closest (except in analyses of SVR) to the nominal time will be used. If there are two observations equally distant to the nominal time, the latest one will be used in analyses. For analyses of SVR (e.g., SVR12), the last value in the window will be used.

If multiple measurements are made on the same day for a safety laboratory parameter, a vital sign parameter, or a flow cytometry parameter, the average of the values will be used to calculate descriptive statistics and in analyses of the mean change from baseline. For summaries of shifts from baseline, graded laboratory values and potentially clinically significant values, multiple values on the same day will not be averaged; all values will be considered for these analyses.

**Table 1. Analysis Time Windows for HCV RNA and Resistance Endpoints, Safety Laboratory and Vital Sign Measurements, Child-Pugh Score, and PRO Instruments (Treatment Period)**

Scheduled Visit	Nominal Day (Study Day)	Time Window (Study Day Range)
Day 1/Baseline a	1 a	≤ 1 a
Week 1	7	2 to 10
Week 2	14	11 to 21
Week 4	28	22 to 42
Week 8	56	43 to 70
Week 12	84	71 to 98
Week 16 b	112	99 to 126
Final Treatment Visit c	2 to ≤ 2 days after last dose of study drug	

a. Day of first dose of study drug.

b. For 16-week treatment only.

c. The last value within the window will be used to define the Final Treatment Visit value. The upper bound of this Final window is Study Drug End Day 2. Study Drug End Day 0 is defined as the day of the last dose of study drug.

Note: For all windows, data must be on or before Study Drug End Day 2. The result closest to the scheduled time point will be used. PRO instruments are collected at Day 1, Week 4 and End of Treatment Visit; Total insulin, Child-Pugh score and alpha fetoprotein are collected at Day 1 and End of Treatment Visit.

**Table 2. Analysis Time Windows for HCV RNA and Resistance Endpoints (Post-Treatment Period)**

Scheduled Visit a	Nominal Day (Study Drug End Day)	Time Window (Study Drug End Day Range)
Post-Treatment Week 4	28	3 to 56
Post-Treatment Week 12	84	57 to 126
Post-Treatment Week 24 b	168	127 to 999
SVR 4 c	28	3 to 56
SVR 12 c	84	57 to 126
SVR 24 b,c	168	127 to 210

a. PT Visits are applicable for subjects who received at least one dose of study drug.

b. Not included in primary CSR.

c. For SVR windows, the last value in the window will be used.

Note: The result closest to the scheduled time point will be used, except for SVR4, SVR12, and SVR24. For all windows, data must occur after Study Drug End Day 2. Study Drug End Day 0 is defined as the day of the last dose of study drug.

**Table 3. Analysis Time Windows for Safety Laboratory and Vital Sign Measurements, Child-Pugh Score, and PRO Instruments (Post-Treatment Period)**

Scheduled Visit a	Nominal Day (Study Drug End Day)	Time Window (Study Drug End Day Range)
Post-Treatment Week 4	28	3 to 56
Post-Treatment Week 12	84	57 to 126
Post-Treatment Week 24 b	168	127 to 999
Final Post-Treatment Visit c	> 2 days after last dose of study drug	

- a. PT Visits are applicable for subjects who received at least one dose of study drug.  
 b. Not included in primary CSR.  
 c. The last value within the PT Period window will be used to define the Final PT Visit value. The lower bound of this Final window is Study Drug End Day 3. Study Drug End Day 0 is defined as the day of the last dose of study drug.

Note: The result closest to the scheduled time point will be used. For all windows, data must occur after Study Drug End Day 2. Vital signs are collected at every PT visit; hematology, chemistry, urinalysis, and coagulation panel are collected at PT Week 4 or PT D/C (if subject discontinued prior to PT Week 4); the coagulation panel, total bilirubin, and serum albumin are also collected at PT Week 12 and PT Week 24; PRO instruments, Child-Pugh score and alpha fetoprotein are collected at PT Week 12 and PT Week 24 (or PT/DC).

**Table 4. Analysis Time Windows for HIV-1 RNA and Flow Cytometry Measurements (Treatment Period)**

Scheduled Visit	Nominal Day (Study Day)	Time Window (Study Day Range)
Day 1/Baseline a	1 a	≤ 1 a
Week 2	14	2 to 21
Week 4	28	22 to 42
Week 8	56	43 to 70
Week 12	84	71 to 98
Week 16 b	112	99 to 126
Final Treatment Visit c	2 to ≤ 2 days after last dose of study drug	

- a. Day of first dose of study drug.  
 b. For 16-week treatment only.  
 c. The last value within the window will be used to define the Final Treatment Visit value. The upper bound of this Final window is Study Drug End Day 2. Study Drug End Day 0 is defined as the day of the last dose of study drug.

Note: Time windows specified in this table are for HCV/HIV co-infected subjects only. For all windows, data must be on or before Study Drug End Day 2. The result closest to the scheduled time point will be used. Flow cytometry samples are collected at Day 1, Week 4, Week 12, and End of Treatment Visit.

**Table 5. Analysis Time Windows for HIV-1 RNA and Flow Cytometry Measurements (Post-Treatment Period)**

Scheduled Visit a	Nominal Day (Study Drug End Day)	Time Window (Study Drug End Day Range)
Post-Treatment Week 4	28	3 to 56
Post-Treatment Week 12	84	57 to 126
Post-Treatment Week 24 b	168	127 to 999
Final Post-Treatment Visit c	> 2 days after last dose of study drug	

- a. Post-Treatment Visits are applicable for subjects who received at least one dose of study drug.  
 b. Not included in primary CSR.  
 c. The last value within the PT Period window will be used to define the Final PT Visit value. The lower bound of this Final window is Study Drug End Day 3. Study Drug End Day 0 is defined as the day of the last dose of study drug.

Note: Time windows specified in this table are for HCV/HIV co-infected subjects only. The result closest to the scheduled time point will be used. For all windows, data must occur after Study Drug End Day 2.

### 6.3 Missing Data Imputation

#### Missing Data Imputation for SVR

HCV RNA values will be selected for analysis based on the analysis windows defined in Section 6.2.

For analyses of SVR, subjects missing visit values will have backward imputation applied, if possible. For backward imputation, if the nearest HCV RNA value after the SVR window is unquantifiable or undetectable, then it will be used to impute the HCV RNA value in the SVR window. If a subject is missing an HCV RNA value within the appropriate SVR window after performing backward imputation, then this value will be imputed with an HCV RNA value from a local laboratory if present; otherwise, the HCV RNA value will be missing. A subject with missing HCV RNA data in the analysis window, after imputations, will be imputed as a failure.

Regardless of the imputation method described above, if a subject starts another treatment for HCV, then all HCV RNA values for this subject measured on or after the start date of the new HCV treatment will be excluded from analyses. The subject will be considered a

failure for summaries of viral response at all time points after the start of the new HCV treatment.

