#### **5.1.2 Modified Intention-to-Treat (mITT) Populations**

Sensitivity analyses of SVR12 as described in Section 10.5, when applicable, will be performed on the ITT population modified to exclude subjects of multiple genotypes according to the central laboratory or phylogenetic analyses or subjects who received incorrect duration of treatment due to incorrect classification of GT or treatment experience at screening (mITT-GT), and on the mITT-GT population modified to exclude subjects who did not achieve SVR12 for reasons other than virologic failure (i.e., subjects with reasons other than on-treatment HCV virologic failure and relapse) (mITT-GT-VF).

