### **Definitions for Efficacy Endpoints**

A confirmed quantifiable value during treatment is defined as any two consecutive HCV RNA measurements  $\geq$  LLOQ (or 100 IU/mL for **Breakthrough**), either both during treatment or at the final treatment measurement and the next consecutive post-treatment measurement. A confirmed quantifiable post-treatment value is defined as any two consecutive post-treatment HCV RNA measurements  $\geq$  LLOQ.

**Breakthrough** = confirmed HCV RNA  $\geq$  100 IU/mL after HCV RNA < LLOQ during the Treatment Period; or confirmed increase from nadir in HCV RNA (two consecutive HCV RNA measurements > 1 log10 IU/mL above nadir) at any time point during the Treatment Period. A single breakthrough value ( $\geq$  100 IU/mL or > 1 log10 above nadir) followed by lost to follow-up also will be considered a breakthrough (i.e., will not require confirmation).

**EOT failure** = HCV RNA  $\geq$  LLOQ at end of treatment with at least 6 weeks of treatment, where the HCV RNA value must be collected on or after Study Drug Day 36 and study drug duration  $\geq$  36 days.

**On-treatment HCV virologic failure** = **Breakthrough** or **EOT failure**; if a subject meets both definitions of **Breakthrough** and **EOT failure**, he or she will be categorized as **Breakthrough** only.

**SVR4** = HCV RNA  $<$  LLOQ in the SVR4 window (4 weeks after the last actual dose of study drug) without any confirmed quantifiable ( $\geq$  LLOQ) post-treatment value before or during that SVR window.

**SVR12** = HCV RNA  $<$  LLOQ in the SVR12 window (12 weeks after the last actual dose of study drug) without any confirmed quantifiable ( $\geq$  LLOQ) post-treatment value before or during that SVR window.

**SVR24** = HCV RNA  $<$  LLOQ in the SVR24 window (24 weeks after the last actual dose of study drug) without any confirmed quantifiable ( $\geq$  LLOQ) post-treatment value before or during that SVR window.

**Relapse12** = confirmed HCV RNA  $\geq$  LLOQ between end of treatment and 12 weeks after last actual dose of study drug (up to and including the SVR12 assessment time point) for a subject with HCV RNA  $<$  LLOQ at Final Treatment Visit who completed treatment and has post-treatment HCV RNA data available, excluding reinfection as described below.

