**Relapse24** = confirmed HCV RNA  $\geq$  LLOQ within the SVR24 window for a subject who achieved SVR12 and has HCV RNA data available in the SVR24 window, excluding reinfection.

**Relapseoverall** = confirmed HCV RNA  $\geq$  LLOQ between end of treatment and up to and including the last HCV RNA measurement collected in the PT Period for a subject with HCV RNA  $<$  LLOQ at Final Treatment Visit who completed treatment and has post treatment HCV RNA data available, excluding reinfection.

Only subjects who have at least one post-treatment HCV RNA value will be included in analyses of relapse. For the analyses of relapse, completion of treatment is defined as a study drug duration of 77 days or greater for subjects assigned to 12 weeks of treatment and 105 days or greater for subjects assigned to 16 weeks of treatment. If the last available post-treatment value is  $\geq$  LLOQ, then the subject will be considered a relapse (i.e., will not require confirmation).

HCV reinfection is defined as confirmed HCV RNA  $\geq$  LLOQ after the end of treatment in a subject who had HCV RNA  $<$  LLOQ at Final Treatment Visit, along with the post-treatment detection of a different HCV genotype, subtype, or clade compared with baseline, as determined by phylogenetic analysis of the NS3 or NS5A, and/or NS5B gene sequences. Reinfection in the case of the same HCV subtype is defined as a clade switch, as indicated by the lack of clustering between the baseline and post-treatment sequences by phylogenetic analysis. If phylogenetic analysis is not possible due to technical difficulties, HCV reinfection may be determined with a confirmed HCV genotype or subgenotype switch by the Versant HCV Genotype Inno-LiPA Assay v2.0 or Sanger assay.

Post-treatment relapse is defined as described earlier (**Relapse12**, **Relapse24**, **Relapseoverall**), and no genotype, subtype, or clade switch compared with baseline as determined by phylogenetic analysis of the NS3 or NS5A gene sequences. If phylogenetic analysis is not possible due to technical difficulties, the subject will be defined as having a post-treatment relapse unless an HCV genotype or subgenotype switch is confirmed by the Versant HCV Genotype Inno-LiPA Assay v2.0 or Sanger assay.

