### **Reasons for SVR12 Non-Response**

Subjects who do not achieve SVR12 (SVR12 non-responders) will be categorized as having:

1. On-treatment HCV virologic failure (see **On-treatment HCV virologic failure** definition; if a subject meets both definitions of **Breakthrough** and **EOT failure**, he or she will be categorized as **Breakthrough** only);
2. Relapse12;
3. Prematurely discontinued study drug with no on-treatment HCV virologic failure (defined as any SVR12 non-responder who prematurely discontinued study drug [study drug duration < 77 days for subjects assigned to 12 weeks of treatment, and < 105 days for subjects assigned to 16 weeks of treatment] and did not meet the **On-treatment HCV virologic failure** definition);
4. HCV reinfection (see definition described earlier) ;
5. Missing follow-up data in the SVR12 window (defined as any subject who completed study drug without data in the SVR12 window after applying the imputation rules and not meeting the definitions of [1], [2], [3], or [4]);
6. Other (defined as any SVR12 non-responder not meeting the definitions of [1] – [5]).

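### A relapse first documented after the SVR12 window is filed as missing data, leaves mITT-GT-VF and is counted as a success in both SAP 10.5.1 imputations, while a late negative value is used

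*SAP*

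**What the plan says.** Protocol 8.1 plans backward imputation for the SVR endpoints and does not limit it by the sign of the later value. SAP 6.3 adds the limit: "if the nearest HCV RNA value after the SVR window is unquantifiable or undetectable, then it will be used". If the window is still empty after that step and after local-laboratory substitution, the rule is: "A subject with missing HCV RNA data in the analysis window, after imputations, will be imputed as a failure".

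SAP 10.1 defines three relapse terms.

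- Relapse12 covers confirmed quantifiable HCV RNA "between end of treatment and 12 weeks after last actual dose of study drug (up to and including the SVR"12 assessment. SAP Table 2 ends the SVR12 window at Study Drug End Day 126.
- Relapse24 looks only inside the SVR24 window (Days 127 to 210) and applies "for a subject who achieved SVR 12 and has HCV RNA data available in the SVR 24 window".
- Relapse_overall runs "between end of treatment and up to and including the last HCV RNA measurement collected in the PT Period".

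The SVR12 non-response list in SAP 10.1 names Relapse12 as its only relapse category. Its missing-data category is "defined as any subject who completed study drug without data in the SVR 12 window after applying the imputation rules" and meeting no earlier category. SAP 5.1.2 removes from mITT-GT-VF the SVR12 non-responders who are "subjects with reasons other than on-treatment HCV virologic failure and relapse".

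SAP 10.5.1 adds two imputations. One carries the last value before the window forward. The other treats non-responders in the premature-discontinuation and missing-data categories as successes.

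**The concern.** A late negative fills the window and a late positive does not. The positive also falls between the two time-limited relapse terms: too late for Relapse12, and barred from Relapse24 because SVR12 was not achieved. A virologic failure that the laboratory has documented is then labelled as a missed visit.

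The stake is mainly mITT-GT-VF, which is meant to isolate virologic failure. It also supplies the stepwise logistic model in SAP 10.6 and the South Korean Fisher tests in SAP 10.8. The SAP 10.5.1 analyses are affected as well, because they would credit a known relapse as a cure. With very few failures expected, the filing of a single subject is visible.

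**Working it through.** **The plan's own figure.** Protocol 8.2 and SAP 4.3 give a 95% interval of 91.6% to 98.4% for 95% of 160. Check: 0.95 ± 1.96 × √(0.95 × 0.05 / 160) = 0.95 ± 0.0338, or 91.62% to 98.38%. It reproduces and is not in dispute.

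**Rule trace.** The subject completed treatment, was below LLOQ at the Final Treatment Visit and at PT Week 4 (Day 28), and has no central or local value in Days 57 to 126. There is no reinfection and no new HCV therapy. The only later sample is at Day 168.

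| Rule | Day 168 ≥ LLOQ | Day 168 < LLOQ |
|---|---|---|
| Backward imputation (6.3) | not applied | applied |
| SVR12, ITT | failure | success |
| Relapse12 (10.1) | no, after Day 126 | no |
| Relapse24 (10.1) | no, SVR12 not achieved | no |
| Relapse_overall (10.1) | yes | no |
| SVR12 reason (10.1) | missing data | not applicable |
| SVR24 reason (10.1) | Other | not applicable |
| In mITT-GT-VF (5.1.2) | no | yes, as success |
| Carry-forward (10.5.1) | success, from PT Week 4 | success |
| Missing treated as success (10.5.1) | success | success |

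The SVR24 reason is Other because a value exists in Days 127 to 210 but no listed category fits. The last-value rule in SAP 10.1 waives confirmation of a relapse. It does not extend the time limit.

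**After Day 210.** Take a subject with SVR12, no value in Days 127 to 210, and one later value. Below LLOQ, it fills the SVR24 window and gives SVR24 success. At or above LLOQ, it is not carried back, the SVR24 reason is missing data, and Relapse24 does not apply.

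**Size if it happens.** Assume 160 treated, 152 with SVR12, no genotype exclusions, all other non-responders non-virologic, and *k* late-documented relapses among the 8 non-responders. Wilson interval: centre (p + z²/2n)/(1 + z²/n), half-width z√(p(1−p)/n + z²/4n²)/(1 + z²/n), with z = 1.96.

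| | mITT-GT-VF SVR12 (Wilson 95% CI) | ITT SVR12 |
|---|---|---|
| SAP as written | 152/152 = 100% (97.5 to 100) | 95.0% |
| kept as failure, k = 1 | 152/153 = 99.3% (96.4 to 99.9) | 95.0% |
| k = 2 | 152/154 = 98.7% (95.4 to 99.6) | 95.0% |
| k = 3 | 152/155 = 98.1% (94.5 to 99.3) | 95.0% |

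If the other 8 − k non-responders are all missing or discontinued, the second 10.5.1 imputation gives 160/160 as written. It gives 159/160, 158/160 or 157/160 (99.4%, 98.8%, 98.1%) once late positives are not credited.

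**How often.** The documents give no missed-visit rate. Assume 1% to 3% of 160 miss PT Week 12 but attend PT Week 24, which is 1.6 to 4.8 subjects. Relapse among cirrhotic subjects in Protocol Tables 6 and 8:

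- all groups: (1 + 2) / (98 + 35 + 19 + 2 + 7 + 64 + 50) = 3/275 = 1.1%;
- highest single group, treatment-experienced GT3: 2/50 = 4.0%.

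Expected subjects: 1.6 × 0.011 = 0.02 to 4.8 × 0.04 = 0.19. The expected shift in mITT-GT-VF is then at most about 0.19 × 0.65 = 0.12 points.

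**The case against.** The best defence is that nothing is lost. The subject fails in the primary ITT analysis either way. SAP 10.7 summarises Relapse_overall by window, with a category after the SVR24 window and subject numbers. SAP 10.4 and 10.5 list reasons for non-response and subjects excluded from mITT-GT-VF. The primary analysis summarises data through PT Week 12 (SAP 4.4), so any effect is mainly in the final CSR. All of that stands.

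The one-way carry-back also has a rationale: a late negative supports an earlier negative, while a late positive does not prove that the subject was positive at Week 12. That supports leaving the SVR12 window empty. It does not support a missing-data label, or imputing success, once the positive is known.

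The wording leaves some room. SAP 5.1.2 says relapse without a subscript, and SAP 10.1 lists Relapse_overall among the post-treatment relapses, so mITT-GT-VF could be read as keeping the subject. But membership turns on the reason for SVR12 non-response, and that list names only Relapse12. Two programmers could differ, which is itself a reason to settle it.

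A reader might infer three stronger points that the documents do not support.

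- *The rules always favour the drug.* Not in ITT, where the subject is a failure.
- *They hide a large share of failures.* Tables 6 and 8 show 4 virologic failures in 281 cirrhotic subjects, or 160 × 4/281 = 2.3, so one subject would be about 1/2.3 = 44%. That supposes the event has occurred, and Relapse_overall and the listings would still show it.
- *The subject belongs in Relapse12.* Protocol 8.1.2.2 limits that endpoint to 12 weeks after the last dose. A first positive at Day 168 is not documented inside it. Absence from relapse after SVR12 is also correct for a subject without SVR12.

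**Conclusion.** The point holds as a misclassification in supportive analyses. A completer with an empty SVR12 window and a first positive afterwards is filed as missing (Other for SVR24), leaves mITT-GT-VF, and becomes a success in both SAP 10.5.1 imputations. The matching late negative is kept as a success. The Day 210 cut creates the same imbalance for SVR24 and Relapse24.

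Primary ITT SVR12 does not change. Few or no subjects are likely to be affected, and the estimate rests on the assumed missed-visit rate. It is probably on the high side, because it applies whole-course relapse rates to subjects already negative at PT Week 4. The case for acting is that the rule runs in one direction in these analyses, its wording can be read two ways, and it is cheap to settle before any such subject is seen.

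**What to change.** Leave the protocol's Relapse12 interval unchanged, and amend the SAP as follows.

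- **5.1.2 and 10.1:** an SVR12 non-responder with no value in the SVR12 window, whose nearest later value is at or above LLOQ, who meets Relapse_overall and is not a reinfection, is a virologic failure and stays in mITT-GT-VF as a failure.
- **10.1, SVR12 and SVR24 reasons:** add a separate category for relapse first documented after the SVR12 window, taking precedence over missing data and Other.
- **10.5.1:** do not impute success under either approach when the nearest later value is at or above LLOQ.
- **10.1, Relapse24:** in subjects with SVR12, count a qualifying value at or above LLOQ from Day 127 onward without the Day 210 cap, and widen the data-availability condition to match.

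The cost is a few sentences and a small programming change, with no new data. The true relapse time stays uncertain for such a subject, and mITT-GT-VF SVR12 may be slightly lower. Without the cap, a subject negative in Days 127 to 210 and positive later would be both an SVR24 responder and a Relapse24 case, so the tables should carry a footnote.
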